1. RESEARCH QUESTIONS

1.1. OVERVIEW OF RESEARCH QUESTIONS

Please state the research question(s) that the evaluation intends to answer and for each research question indicate the type: implementation or outcome.

- *Implementation Questions: Identifying whether a program has been successful in attaining desired implementation goals (e.g., reaching intended target population, enrolling intended number of participants, delivering training and services in manner intended, etc.)*
- *Outcome Questions: Identifying whether program is associated with intended outcomes for participants (e.g., do participants' knowledge, attitudes, behaviors, or awareness change?)*

Research questions in this study are framed by a Random Control Trial (RCT) design that will be used to determine if *TCD Project* participants who receive *enhanced TCD services* (treatment) derive more benefits than those who receive only *standard TCD services* (control), and they guide two types of analyses in this study—impact and implementation (see Table 1.1 below). Impact analyses estimate the primary benefits of participation for different service conditions six months after TCD enrollment. Primary benefits refer to outcomes that indicate improved attitudes and behavior for healthy

family relationships (parent, co-parent, and partner). However, strong conclusions can only be drawn about the benefits of participation when impact estimates are made after full or nearly full implementation of TCD services. Conclusions are more difficult to draw for impact estimates that are made when participants do not receive the intended service amounts. Consequently, implementation analyses place impact estimates in the appropriate context for interpretation by considering the extent to which TCD services are fully implemented for participants in both study groups.

Table 1.1: Research questions by type for the impact study, implementation and outcome

No	Research Question	Implementation or Outcome?
I1	To what extent were the enrollment targets for the TCD Project achieved for the treatment and control groups?	Implementation
I2	To what extent were the intended amounts of standard TCD services (TYRO Dads, Core Communication curricula) offered to and received by the control group?	Implementation
I3	To what extent were the intended amounts of enhanced TCD services (TYRO Dads, Core Communication, Ray of Hope curricula) offered to and received by the treatment group?	Implementation
I4	To what extent did the CQI Team carry out the steps in the CQI Plan each program year?	Implementation
R1	What is the impact of enhanced TCD services (treatment) compared to standard TCD services only (control) on healthy parenting attitudes immediately following program completion?	Outcome
R2	What is the impact of enhanced TCD services (treatment) compared to standard TCD services (control) only on healthy partner relationship behaviors 6 months after TCD enrollment?	Outcome
R3	What is the impact of enhanced TCD services (treatment) compared to standard TCD services only (control) on healthy parenting behavior 6 months after TCD enrollment?	Outcome
R4	What is the impact of enhanced TCD services (treatment) compared to standard TCD services only (control) on healthy co-parenting behavior 6 months after TCD enrollment?	Outcome
R5	Does the impact of the Ray of Hope hours vary by ethnicity?	Secondary outcome

* you may add rows by hitting the tab button, or right click and select insert row below

1.2. OUTCOME RESEARCH QUESTIONS

For each outcome research question listed above, whether a descriptive or impact design, summarize the inputs (e.g., program components, program supports, implementation features, etc.), target population (e.g., the population for which the effect will be estimated) and the outcomes (e.g., child well-being, father-child engagement, etc.) that will be examined to answer the research question(s). Comparisons for descriptive evaluations may reflect circumstances before the grant, pre-treatment, or pre-determined benchmark from other studies with similar interventions.

Research Question Number	Intervention	Target Population	Comparison	Outcome	Confirmatory or Exploratory?
R1	Ray of Hope curriculum (10 hours) that focuses on domestic violence and related risk factors	Latino fathers: low-income, 18+ years, no open criminal cases (or deferred), children up to 24 years	Parenting attitudes for the treatment group to the control group immediately after completing TCD program.	Healthier parenting attitudes for the Treatment Group that receives enhanced services.	Confirmatory
R2	Ray of Hope curriculum (10 hours) that focuses on domestic violence and related risk factors	Latino fathers: low-income, 18+ years, no open criminal cases (or deferred), children up to 24 years	Partner relationship behaviors for the treatment group to the control group 6 months after TCD enrollment.	Healthier partner relationship behaviors for the Treatment Group that receives enhanced services.	Confirmatory
R3	Ray of Hope curriculum (10 hours) that focuses on domestic violence and related risk factors	Latino fathers: low-income, 18+ years, no open criminal cases (or deferred), children up to 24 years	Parenting behavior for the treatment group to the control group 6 months after TCD enrollment.	Healthier parenting behavior for the Treatment Group that receives enhanced services.	Confirmatory
R4	Ray of Hope curriculum (10 hours) that focuses on	Latino fathers: low-income, 18+ years, no open criminal	Co-parenting behavior for the treatment group to the	Healthier co-parenting behavior for the Treatment	Confirmatory

	domestic violence and related risk factors	cases (or deferred), children up to 24 years	control group 6 months after TCD enrollment.	Group that receives enhanced services.	
--	--	--	--	--	--

* you may add rows by hitting the tab button, or right click and select insert row below

2. BACKGROUND

For each outcome research question listed in 1.1, whether descriptive or impact design, briefly summarize the previous literature or existing research that informs the stated research question and how the evaluation will expand the evidence base. Explain why the research questions are of specific interest to the program and/or community. Only a short summary paragraph description is needed below. Additional documentation, such as a literature review, may be appended to this document.

Research Topic	Existing Research	Contribution to the Evidence Base	Interest to Program and/or Community
R1: Healthy Parenting Attitudes	Participants in fatherhood programming, particularly those in the target population, may not be receiving sufficient supports to address domestic violence and related risk factors in their families	Determine whether using curriculum to directly address the negative attitudes, expectations, and behaviors associated with domestic violence can enhance program participation benefits related to parenting attitudes among the target study population	Inform practitioners about whether the dynamics of domestic violence can be addressed directly with curriculum when trying to build parenting skills among program participants
R2: Healthy Partner Relationship Behaviors	Participants in fatherhood programming, particularly those in the target population, may not be receiving sufficient supports to address domestic violence and related risk factors in their families	Determine whether using curriculum to directly address the negative attitudes, expectations, and behaviors associated with domestic violence can enhance program participation benefits related to partner relationship behaviors among the target study population	Inform practitioners about whether the dynamics of domestic violence can be addressed directly with curriculum when trying to build healthy partner relationship skills among program participants
R3: Healthy Parent Behavior	Participants in fatherhood programming, particularly those in the target population, may not be receiving sufficient supports to address domestic	Determine whether using curriculum to directly address the negative attitudes, expectations, and behaviors associated with domestic violence can enhance program participation	Inform practitioners about whether the dynamics of domestic violence can be addressed directly with curriculum when trying to build healthy

	violence and related risk factors in their families	benefits related to parenting behaviors among the target study population	parenting skills among program participants
R4: Healthy Co-parent Behavior	Participants in fatherhood programming, particularly those in the target population, may not be receiving sufficient supports to address domestic violence and related risk factors in their families	Determine whether using curriculum to directly address the negative attitudes, expectations, and behaviors associated with domestic violence can enhance program participation benefits related to co-parenting behaviors among the target study population	Inform practitioners about whether the dynamics of domestic violence can be addressed directly with curriculum when trying to build healthy co-parenting skills among program participants

* you may add rows by hitting the tab button, or right click and select insert row below

3. LOGIC MODEL

Clearly demonstrate how the research question(s) (and the related implementation features and/or participant outcomes) link to the proposed logic model and the theory of change for the program. You may append a copy of your logic model to this document.

MER and Anthem Strong Families worked together to create a logic model to specify a theory of change for delivering *standard* and *enhanced TCD services*. Service delivery processes specified in the model are linked to the desired outcomes that promote healthy family relationships and economic stability. Model specification incorporates an RCT study design to conceptualize service delivery to make impact estimates for the TCD Project by comparing primary and secondary participant outcomes between study groups after random assignment. Treatment group participants receive *enhanced TCD services* and control group participants receive *standard TCD services*.

Service delivery processes: Key aspects of service delivery processes in the theory of change—goals, inputs, activities, and outputs—articulate the experiences that are designed to solve specific problems for those who agree to participate in the TCD Project. Solving each problem identifies three broad service delivery goals to maximize participation benefits for study groups as explained below:

- **Goal 1 - Deliver standard TCD services to the Control Group:** Candidates randomly assigned to the control group will understand they receive *standard TCD services* to develop their skills to engage in healthy behaviors for parenting, co-parenting, partner relations, employment, and financial management but only after receiving an orientation about the TCD Project and giving project staff informed consent to participate in study activities. Then, *TYRO Dads and Core Communication* will be delivered to the control group as well as support services through case management and the *ASF Mini-Clinic*, as needed

- **Goal 2 - Deliver enhanced TCD services to the Treatment Group:** Candidates randomly assigned to the treatment group will understand they receive *enhanced TCD services* to develop their skills to engage in healthy behaviors for parenting, co-parenting, partner relations, employment, financial management and address the dynamics of domestic violence, but only after receiving an orientation about the TCD Project and giving project staff informed consent to participate in study activities. Then, the *Ray of Hope* curriculum will be delivered only to the treatment group as well as the *TYRO Dads* and *Core Communication* curricula and support services through case management the *ASF Mini-Clinic*, as needed, under a shared condition with the control group.
- **Goal 3 - Conduct Continuous Quality Improvement (CQI) to ensure full implementation of *standard* and *enhanced TCD services* for study groups:** Reports prepared and presented to the CQI Team by evaluators will use a series of performance indicators to track key outputs over time to identify any *TCD services* delivered to study groups that might fall short of the intended amounts to be offered (i.e., fidelity standards) and received (i.e., dosage thresholds) by them. The CQI Team will then work with project staff to develop and implement performance interventions to address any outputs that need improvement to ensure the services offered to and received by participants meet the intended amounts by the end of each program year.

Desired Outcomes: Outcomes specified in the logic model theorize the primary outcomes that are desired for participants in each study group after they receive either *standard* or *enhanced TCD services*. All outcomes specified in the logic model are theorized to be more positive for parents assigned to the treatment group because they receive *enhanced TCD services*, whereas the control group receives *standard TCD services*.

4. HYPOTHESES

For each specified research question, state the hypothesized result(s) and briefly describe why these results are anticipated.

Research Question	Hypothesized Result
R1	
The treatment group will report healthier parenting attitudes than the control group immediately after completing the TCD program.
 
Both study groups receive TYRO Dads and Core Communication curricula under a shared condition to build healthy parenting skills, but only the treatment group receives the Ray of Hope curriculum, which directly addresses the dynamics of domestic violence and related risk that can negatively impact healthy family relationships.

R2	
The treatment group will report healthier partner relationship behaviors than the control group six months after TCD enrollment.
 
Both study groups receive TYRO Dads and Core Communication curricula under a shared condition to build healthy communication skills, but only the treatment group receives the Ray of Hope curriculum, which directly addresses the dynamics of domestic violence and related risk that can negatively impact healthy family relationships.

R3	
The treatment group will report healthier parenting behavior than the control group six months after TCD enrollment.
 
Both study groups receive TYRO Dads and Core Communication curricula under a shared condition to build healthy parenting skills, but only the treatment group receives the Ray of Hope curriculum, which directly addresses the dynamics of domestic violence and related risk that can negatively impact healthy family relationships.

R4	
The treatment group will report healthier co-parenting behavior than the control group six months after TCD enrollment.
 
Both study groups receive TYRO Dads and Core Communication curricula under a shared condition to build healthy co-parenting skills, but only the treatment group receives the Ray of Hope curriculum, which directly addresses the dynamics of domestic violence and related risk that can negatively impact healthy family relationships.

* you may add rows by hitting the tab button, or right click and select insert row below

5. RESEARCH DESIGN

For each research question, briefly describe why the research design proposed will answer each research question(s). State whether the proposed evaluation is a descriptive or impact evaluation and justify why the proposed research design is best suited to answer the research question(s).

Research Question	Design	Justification
R1	Random assignment will isolate the effect on parenting attitudes from the Ray of Hope curriculum delivered to the treatment group.	Healthy parenting attitudes are compared between study groups where the only difference between them is whether participants receive the Ray of Hope curriculum because both groups will receive TYRO Dads , Core Communication , and support services under a shared condition.
R2	Random assignment will isolate the effect on partner relationship behaviors from the Ray of Hope curriculum	Healthy partner relationship behaviors are compared between study groups where the only difference between them is whether participants receive the Ray of Hope curriculum because both groups will receive TYRO Dads , Core

	delivered to the treatment group.	Communication , and support services under a shared condition.
R3	Random assignment will isolate the effect on parenting behavior from the Ray of Hope curriculum delivered to the treatment group.	Healthy parenting behavior will be compared between study groups where the only difference between them is whether participants receive the Ray of Hope curriculum because both groups will receive TYRO Dads , Core Communication , and support services under a shared condition.
R4	Random assignment will isolate the effect on co-parenting behavior from the Ray of Hope curriculum delivered to the treatment group.	Healthy co-parenting behavior are compared between study groups where the only difference between them is whether participants receive the Ray of Hope curriculum because both groups will receive TYRO Dads , Core Communication , and support services under a shared condition.

* you may add rows by hitting the tab button, or right click and select insert row below

6. ONGOING GRANTEE AND LOCAL EVALUATOR COORDINATION

Describe how the grantee and local evaluator collaboratively worked together to identify the research question(s) and research design to ensure its feasibility and relevance. Describe how the grantee and local evaluator will continue to work together throughout the evaluation to proactively address unforeseen challenges as they arise and ensure the rigor and relevance of the evaluation and its findings. Describe how the grantee and local evaluator will coordinate dissemination efforts. Describe how these processes will occur while maintaining the independence of the evaluation.

The basis for ongoing coordination between ASF (the grantee) and MER (the local evaluator) is regular, systematic communication through a structure comprised of recurring meetings and daily interactions with embedded staff. Throughout the original proposal process, and now during the evaluation planning phase, MER worked in consort with ASF to design a study with research questions that are appropriate to the intervention. MER guides the process, given our experience designing and running evaluations, and ASF provides expertise on their community, target population, and program/curricula specifics.

Recurring meetings will include a bi-weekly project CQI team meeting. Under the leadership of the Data Manager and Lead MER Evaluator, the CQI team reviews data from the nFORM and local evaluation systems to identify and mitigate implementation or data issues, and closely examine trends and accomplishments. This team includes ASF organizational and project leadership, the MER Evaluation team, and front-line staff representatives (e.g., Facilitators, Case Managers).

In addition to CQI team meetings, overall project team meetings occur monthly (at a minimum), with project leaders across MER and ASF in attendance, to ensure the partnership remains strong and that coordination across organizations is on track. This

recurring, ongoing meeting structure is conducive to close coordination, ensuring that challenges can be quickly addressed, and promising strategies can be efficiently maximized.

One of the key components of this coordination effort is the CQI Data Manager, who is a MER employee embedded with ASF. The Data Manager functions to bridge the gap between organizations. They will interact with ASF staff daily while completing their job duties and play a leadership role in the recurring meetings outlined above. See Section 8 below for more details about this role and others. Both the meetings and the roles outlined above will continue throughout the entire project period, providing opportunities to ensure the rigor and relevance of the evaluation and its findings, and to discuss and coordinate dissemination efforts (which will also be shared across MER and ASF).

MER has a great deal of experience conducting impact studies with RCT designs using this exact process for other projects funded by the OFA. Clearly outlining roles and responsibilities maintains the independence of the evaluation. That is, the evaluation team helps identify and illuminate areas of concern or improvement (for the program and the evaluation), but the program staff have responsibility for implementing improvements and providing direct services to participants. In this way, ASF and MER acknowledge our shared interest in and responsibility for a well-executed project and evaluation, but that MER is also an independent and external organization with a high level of integrity and is not responsible for nor invested in the specific outcomes of the program. This allows for close coordination without allowing for co-dependence, or for personal interests to influence evaluation findings.

7. IMPACT EVALUATIONS ONLY: METHODS TO DEVELOP STUDY GROUPS

If the research design includes the comparison of two or more groups (e.g., a program group and a comparison group), please specify how the groups will be formed and describe the programming for which each will be eligible and how they differ below. The control/comparison group and the program/treatment group should be assigned using a systematic approach appropriate to the research design. Note: If the research question(s) and study design do not necessitate comparisons, this issue does not need to be addressed.

Specify how the groups will be formed.

Study groups will be formed using IRB approved procedures for random assignment after enrollment into the TCD. After soliciting informed consent, participants who agree to participate in the study provide case managers with signed consent forms. After documenting consent, the CQI Data Manager randomly assigns participants to achieve an even distribution across the treatment and control groups. *Assignments are made and then recorded onto the nFORM data collection system by selecting cards*

	
that are organized into a stack that equals the number of parents who attended an orientation and now wish to receive TCD services and participate in the impact study. Cards in the stack have equal amounts of even and odd numbers depicted on them and one is drawn for each study participant. Selections into either the treatment or control group depended on whether a participant receives an even or odd number.

Please describe the comparison/control group experience – that is, the types of services available to the comparison/control group.
	
Fathers assigned to the control group do not receive enhanced TCD services. Instead, they receive the same standard services—TYRO Dads and Core Communication—and support services as treatment group parents under a shared condition (see the theory of change logic model mentioned above). Standard TCD service experiences for the control group should be the same as the treatment group. Parents assigned to both groups are offered the same number, schedule, and duration of workshop offerings for TYRO Dads and Core Communication curricula and attend them together, so they experience the same instructional practices that deliver the same curricula content.


How will the control/comparison group experience differ from the program group's experience?
	
Only the treatment group receives the Ray of Hope curriculum as a service enhancement to directly address the dynamics of domestic violence and related risk in families (see the theory of change logic model for dosage and schedule).

Please list any other services that are similar to the services your program offers and are available in the areas where your program will operate.
	
Anthem Strong Families (ASF) is the only non-profit in its designated service area offering a complete level of extensive fatherhood education and support services to community fathers and spouses of children up to 24 years old free of charge. There are other smaller ministries or service providers that target fathers of newborns offering periodic workshops for new dads but none on a continuous basis as ASF. The service area for ASF is adjacent to Tarrant County/Ft. Worth, TX., home of the longest existing fatherhood coalition in Texas that provides services to Tarrant County and DFPS Region 3-W.

Are there plans to offer the program to individuals in the control/comparison group in the future? If so, please indicate when they will be offered to participate in the intervention.
	
No.

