7.1. RANDOM ASSIGNMENT TO DEVELOP STUDY GROUPS

If groups will be constructed by random assignment, please describe the process of random assignment and how random assignment will be monitored to prevent crossover of those assigned to specific study groups (e.g., individuals assigned to the comparison group who receive treatment) by addressing the questions below.

Who will conduct random assignment?	Eligible fathers who wish to participate in the study are randomly sorted into a treatment or control group by the CQI data manager or by case managers under supervision of the CQI Data Manager. The CQI Data Manager is trained by Senior staff and overseen by a Senior Consultant from MER.
When does random assignment occur (e.g., before or after enrollment)?	Orientation attendees who express interest in TCD services return the following week to enroll at their respective recruitment sites. Those who are also willing to participate in the impact study provide signed consent forms before they are assigned to study groups. After consent is documented, parents are randomly sorted into either a treatment or control group.
How and when are study participants informed of their assignment status?	Participants will be informed of their assignment status immediately after randomization.
Will groups be stratified in any way to ensure balance between treatment and control? If yes, what characteristics or methods will be used?	No.
What strategies will be used to ensure there is no re-assignment or non-random assignment to the treatment group?	A C2 (i.e., client profile) is entered onto nFORM to create a client profile for eligible parents who attend orientations for the TCD Project. Parents who return to participate in the study have their study group assignment entered onto nFORM. Only parents assigned to the treatment group as noted on nFORM can register and attend Ray of Hope workshops. Study group assignment cannot be changed once it has been noted on nFORM.

What strategies will be used to minimize crossovers?	The nFORM system produces an operational report that specifies study group assignment for all parents who agree to participate in the study. Study group assignment as noted on nFORM will be examined with the relevant operational report during CQI-Team meetings to make sure participants receive the services specific to their study group.

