Chi-Square and 2-sample t-tests assess baseline equivalency of study groups by analyzing pre-survey responses to items that describe the characteristics of participants and their developmental starting points before receiving TCD services. Participant characteristics—such as demographics, family structure, and socioeconomic background—are reported on the nFORM ACS Survey. Developmental starting points refer to the attitudes and behavior exhibited before TCD participation and are reported on the nFORM Community Fathers Entrance Survey and OLLE Pre-survey. Chi-Square tests are run for

categorical and dichotomous variables, such as relationship status (e.g., married, single, divorced) or whether a participant reports having a savings account (i.e., yes/no). Two-sample t-tests are run for interval and continuous variables, such as the number of children in a household, or levels of agreement with healthy parenting attitudes. Any differences detected across study groups are incorporated into the model as co-variates.

Study group assignment (1=treatment, 0=control) is repeatedly regressed against the dependent variables to model comparisons of outcomes constructs between study groups (see the table below). Co-variates specified in the model will control for the influence of any significant baseline differences between study groups that were detected in the baseline equivalency analyses for demographics, family structure, socioeconomic background, and developmental starting points.

Procedures to run the linear regression model rely on standard regression to model the influence of study group assignment on dependent variables. All dependent variables are continuous, such as when participants report how many hours they spend with their child or respond to multiple items in a scaled construct by indicating levels of agreement with statements about key parent attitudes.

Benefits of the Ray of Hope curriculum will confirm hypotheses if respondents assigned to the treatment group report greater improvements in outcomes ($p < .05$) than those in the control group for each outcome measure identified above.

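### The 0.2 SD detectable effect at 80% power holds only without the planned Bonferroni correction and must be restated; secondarily, the model described in the SAP ignores the card stacks and the treatment-only Ray of Hope classes

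*Protocol*

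**What the plan says.** **Power.** The table in Protocol section 9.3 uses a one-tailed 0.05, 80% power, 620 analysed fathers and a minimum detectable effect size of 0.2 for each of four outcomes. The rows for outcome SD and for variance explained by covariates are blank, and the cluster-trial rows are marked not applicable. Section 9.2 splits the 620 as 310 per arm, from 443 randomised per arm.

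**Multiplicity.** The SAP (Data Analysis, Analytic approach) plans a Bonferroni correction and limits modelling to six outcomes. The same paragraph says Type II error is controlled by adequate power. It gives no divisor. Protocol section 1.2 marks four questions, R1 to R4, as confirmatory.

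**Assignment.** In Protocol section 7 the cards form "a stack that equals the number of parents who attended an orientation" and who wish to join the study, and "Cards in the stack have equal amounts of even and odd numbers depicted on them and one is drawn for each study participant". Section 7.1 answers no to stratification.

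**Delivery.** For the standard curricula the two arms "attend them together, so they experience the same instructional practices that deliver the same curricula content" (section 7). For Ray of Hope, "Only parents assigned to the treatment group as noted on nFORM can register and attend" (section 7.1). For its timetable section 7 tells the reader to "see the theory of change logic model for dosage and schedule".

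**Analysis.** The SAP states: "Procedures to run the linear regression model rely on standard regression to model the influence of study group assignment on dependent variables". Its covariate rule is: "Any differences detected across study groups are incorporated into the model as co-variates". The characteristics it tests are demographics, family structure, socioeconomic background and developmental starting points.

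**The concern.** The power statement and the planned test do not use the same significance level. A reader of section 9.3 would take a null result to mean that an effect of 0.2 SD had been given an 80% chance of detection. Under the correction the SAP plans, that chance is not much better than even.

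The secondary issue is the standard error. If each orientation's stack is used up in equal halves, orientation is a blocking factor. Leaving it out makes the model standard error slightly too large. Fathers taught together in Ray of Hope classes may resemble each other, and this happens in one arm only. Ignoring that makes the standard error too small. The covariate rule would not pick up the stack, because it is not among the characteristics tested and is balanced by design.

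**Working it through.** **1. Reproduce the stated figure.** Inputs: n = 310 per arm (section 9.2); one-sided α = 0.05 and power 80% (section 9.3); SD 1; no covariates; independent fathers.

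SE = √(2/310) = 0.0803. MDES = (1.645 + 0.842) × 0.0803 = 0.1997. This matches 0.2. A two-sided uncorrected 0.05 would need 786 fathers and does not match.

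**2. Apply the planned correction.** With divisor k, MDES = (z at 1 − 0.05/k + 0.842) × SE. Power at 0.2 SD = Φ(0.2/SE − z), where 0.2/0.0803 = 2.490.

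| Divisor | z | MDES | Power at 0.2 SD |
|---|---|---|---|
| 1 (section 9.3) | 1.645 | 0.1997 | 80.1% |
| 4 (confirmatory questions) | 2.241 | 0.248 | 59.8% |
| 6 (SAP outcomes) | 2.394 | 0.260 | 53.8% |

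Keeping 0.2 at 80% power would need 2 × ((z + 0.842)/0.2)² = 476 analysed per arm with four tests, or 524 with six. Both exceed the 443 to be randomised per arm, so better retention cannot close the gap.

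**3. Secondary point, in closed form.** Let rb be the orientation ICC (both arms), rc the class ICC (treatment arm only) and m the analysed fathers per class. Assume one class per stack and equal analysed numbers by arm. True over model variance is VR = [(1 − rb) + (1 − rb − rc) + rc·m]/2, and actual one-sided error is 1 − Φ(1.645/√VR). The documents give none of rb, rc or m, so all are assumed.

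- rb 0.10, rc 0: VR = 0.90, error 4.1%
- rb 0.10, rc 0.05, m 5: VR = 1.00, error 5.0%
- rb 0.05, rc 0.05, m 8: VR = 1.125, error 6.0%
- rb 0.10, rc 0.05, m 12: VR = 1.175, error 6.5%
- rb 0, rc 0.10, m 12 (the extreme examined): VR = 1.55, error 9.3%

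**4. Secondary point, by simulation.** 20,000 replicates per setting; stacks of 10/20/30 randomised; each father retained with probability 310/443; nominal one-sided 5%; Monte Carlo error about ±0.3 points.

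| rb, rc | SAP model | Cohort fixed effect, cohort-clustered SE |
|---|---|---|
| 0.10, 0 | 4.4/4.4/4.5% | 4.9/5.0/5.1% |
| 0.05, 0.02 | 5.0/5.1/5.5% | 5.0/4.9/5.0% |
| 0.10, 0.05 | 4.8/5.5/6.6% | 4.8/4.8/4.9% |
| 0, 0.05 | 5.4/6.2/7.0% | 4.8/5.0/5.0% |

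A cohort fixed effect with model-based standard errors, at 0.10 and 0.05, gave 5.4/6.2/7.4%. That is worse than the SAP model, because it removes the conservative part and keeps the liberal one.

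If each class pools two orientations (0.10 and 0.05), the SAP model gives 5.7/7.3/8.3%. Clustering by single orientation gives 5.7/6.4/6.7%, and clustering by the set of orientations sharing a class gives 4.9/5.1/5.0%.

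**5. Would the covariate rule catch the stack?** In 1,500 simulated trials at each of three stack sizes, with 30% random loss, a test of stack against arm was never significant.

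**The case against.** **On power.** Covariate adjustment could recover precision, and section 9.3 leaves that row blank. To restore 0.2, covariates would have to explain 1 − (0.2/0.248)² = 35% of the variance with four tests, or 1 − (0.2/0.260)² = 41% with six. The SAP adds only covariates that differ between arms at baseline, so it does not guarantee even the baseline outcome. The divisor is also not settled. Neither objection rescues the stated figure, since both candidate divisors give power below 60%.

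**On clustering, the case against is strong and mostly stands.** Every ICC, stack size and class mapping is assumed. Over much of the range the SAP model is close to nominal. Excess false positives need class effects alongside an average effect of zero. One stack per orientation is the natural reading of section 7, but it is an inference: an odd count cannot split equally, and section 7.1 denies stratification. The remedy also has a price. With no clustering and stacks of 10/20/30, power at 0.2 SD falls by 1.8/1.8/2.1 points at 0.05 and by 3.6/4.1/5.3 at 0.05/6. With stacks of 4 the loss is about 5–6 and 8–9 points; one run went from 80.1% to 75.0% and from 54.2% to 46.4%. With ICCs of 0.10 and 0.05, power at 0.05/6 goes from 54.4/53.6/54.7% to 52.1/47.5/43.3%, part of which is the cost of a correct standard error. These losses are why a sensitivity analysis is an acceptable minimum.

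**Stronger readings a reader might infer.** One is that the trial's false-positive rate is inflated. The documents do not fix even the direction. Another is that randomisation is compromised or the estimate biased. Nothing supports that. A third is that the not-applicable ICC entry is an error. It answers a row meant for cluster trials, and fathers are randomised individually. Finally, the missing stack or class term is established for the SAP prose only: a table the SAP points to and the logic model holding the Ray of Hope schedule are not in the text available.

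**Conclusion.** The power statement does not describe the planned test. This conclusion needs no ICC assumption. It takes the protocol's own 310 per arm, one-sided testing and absence of covariate gain, and gives a detectable effect of 0.248 or 0.260 SD in place of 0.2, with power at 0.2 SD of 59.8% or 53.8% in place of 80%. It does not show that the trial will miss a real effect, whose size is unknown.

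The omission of stack and class is a lesser matter of standard errors. With one class per stack and class ICCs up to 0.05, error is about 4–7% at nominal 5%, with the sign unknown. It goes higher only under a larger class ICC or classes pooled across orientations, neither of which the documents report. That justifies prespecifying an answer, but not a claim that the SAP model is invalid.

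**What to change.** 1. Restate the minimum detectable effect and power in Protocol section 9.3 and in the SAP's Type II error paragraph at the Bonferroni level. Name the divisor and the tests it counts, and note that independent fathers are assumed. This is wording only.

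2. Confirm whether a stack or orientation identifier is kept. nFORM holds group assignment and workshop attendance, but no section says the stack is recorded. If it is not, the sponsor should say whether the cohort can be rebuilt, for instance from enrolment date and site.

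3. If it can, prespecify for each outcome a model with an orientation-cohort fixed effect and standard errors clustered by cohort, with cohorts minus 1 degrees of freedom, at least as a sensitivity analysis. Where Ray of Hope classes pool whole orientations, cluster by the set of cohorts sharing a class. Do not add the cohort term with model-based standard errors alone. The cost is a data step plus the power losses given above if there is no clustering. The SAP is dated 12/9/2024 and follow-up surveys are scheduled to 05/31/25, so this can be settled before follow-up data are complete.

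4. Clarify what the negative answer on stratification in section 7.1 covers, given the balanced card stacks in section 7, and how odd counts are handled.
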